14.6. Protocol Modifications

The Investigator will not modify this protocol without obtaining the concurrence of Pulmotect. All protocol amendments will be issued by Pulmotect, and must be signed and dated by the Investigator prior to implementation of the amendment. Pulmotect will submit protocol modifications to regulatory agencies as required by 21 CFR 312.30. The Investigator is responsible for notifying the IRB/ethics committee of changes. Any changes that potentially affect subject safety or significantly alter the conduct of the study (e.g., changes to inclusion or exclusion criteria, study drug dosage, study procedures, etc.) must have written approval prior to implementation.

Note: The IRB/ethics committee may require the informed consent form be revised to reflect the study revisions.

In situations requiring a departure from the protocol for a subject that has been enrolled appropriately, the Investigator or other physician in attendance will contact Pulmotect by telephone. If possible, this contact will occur before implementing any departure from the protocol. In all cases, contact must be made as soon as possible in order to discuss the situation and agree on an appropriate course of action. The source documents must reflect any departure from the protocol and be transcribed into the eCRF. The investigator is responsible for notifying the IRB/ethics committee of any departures from the protocol.

No requests for a waiver from the specified inclusion/exclusion criteria will be granted.

14.7. Data Collection

Study data will be entered into an EDC system (eCRFs). Subject screening information will be recorded by the study site. The following will be the minimum captured: initials, subject personal identification number, date of screening, and enrollment status.

Data collected through the completion of experimental procedures required by this protocol will be recorded in the subject's source documentation. These data will then be transcribed into the eCRF.

All required study data will be entered into the eCRFs provided by Pulmotect. All study data should be entered into the eCRF as soon as possible after collection. All information in the eCRFs must be supported by original data in the subject's medical records. All medical records, laboratory printouts, notes made by the physician, and other materials such as x-rays will be considered source data and must be available for inspection by Pulmotect, its designees, or regulatory authorities.

Appropriate training of the study site will be conducted prior to study initiation to assist with making entries and corrections to data entered into an eCRF. The Investigator remains responsible for the accuracy and adequacy of all data entered into the eCRFs (EDC system).

Data will be monitored as described in Section 14.9. Data entered into eCRFs will be reviewed and compared with source documents by monitors that are adequately trained using the EDC system.

Upon further data processing, queries may be generated and sent electronically to the Investigator for clarification or correction. The Investigator or designee will address any queries and provide resolution within the EDC system.

The eCRF will be signed (electronically) by the Investigator after review (date and time will be captured in the eCRF audit trail). After completion of the study, completed eCRFs will be electronically transferred to Pulmotect and/or designee and stored in the archives according to the data management plan. Once the eCRFs are signed by the Investigator, the data manager will lock the eCRFs for data analysis.

14.8. Maintaining Records

A Site Regulatory Binder must be maintained at the investigative site and will contain the documents identified in the list of Essential Documents according to ICH GCP, including a signed Investigator Agreement. Pulmotect, or its designee, will provide a Site Regulatory Binder to the site.

According to the United States Federal Regulations (21 CFR 312.57[c]), all records and reports related to this clinical study must be retained by the Investigator for at least 2 years after approval of a marketing application and until there are no pending or contemplated marketing applications or until at least 2 years have elapsed since the formal discontinuation of clinical development of the investigational product. Pulmotect will inform the Investigator as to when these documents no longer need to be retained. These documents must be stored in a secure archive and be available in the event of a regulatory audit.

Study records that must be retained in the Site Regulatory Binder (or the Pharmacy Manual, if appropriate) may include, but are not necessarily limited to: study personnel identification, designation and signature list, subject screening records, subject roster (names omitted), protocol and any amendments or administrative changes, product disposition records, essential documents identified in ICH GCP guidelines, correspondence, laboratory accreditations, and normal laboratory ranges. The site must keep the binder current and available along with relevant subject charts and study reports for review by the Sponsor, IRB/Ethics Commitee, FDA, and/or local regulatory authorities.

14.9. Monitoring, Auditing, and Inspecting

Pulmotect or its designee will monitor all aspects of the study with respect to current GCP and standard operating procedures for compliance with applicable regulations and to ensure that the rights of subjects are protected. Pulmotect or a designee (e.g., clinical research organization) will assure the accuracy of the data and the selection of a qualified Investigator and appropriate study center. The protocol procedures will be reviewed with the Investigator and associated personnel prior to study initiation and during periodic monitoring visits. Pulmotect or a designee will review eCRFs for accuracy and completeness during onsite monitoring visits. Discrepancies will be resolved with the Investigator or designee as appropriate.

Remote monitoring may be conducted as required to identify trends and issues, evaluate enrollment status, query status, data quality, AEs, etc.

Pulmotect or its designees will monitor the study using the following methods:

- Frequent telephone contacts
- Periodic site visits
- Review of original subject records, eCRFs, drug accountability and storage, and general study documentation

To ensure the study can be adequately monitored, the Investigator will cooperate in providing Pulmotect, or Pulmotect's designee, with direct access to all study source documents (e.g., subject charts and study files) and responding to inquiries that may arise as a result of the document review.

Review of these documents will usually occur during a routine monitoring visit but may also be required during a visit by a quality assurance auditor. The Investigator will also provide direct access to these records to regulatory representatives if and when requested. Pulmotect reserves the right to terminate the study if access to source documentation of work performed in this study is denied to the Pulmotect, its designee, or regulatory representatives.

14.10. Confidentiality

The anonymity of subjects participating in this study must be maintained. Subjects will be identified by their assigned number and their initials in all written communications between the Investigator and Pulmotect, or Pulmotect's designee. Documents that are not submitted to Pulmotect and that identify the subject (e.g., signed informed consent, source documents/charts) will be made available to Pulmotect or regulatory authorities for inspections, but will be maintained in confidence.

All study-related information provided by Pulmotect to the Investigator and not previously published, including but not limited to the active study agent identity, the Investigator's Brochure, the study protocol, verbal and written communication, eCRFs, assay methods, and scientific data, will be considered confidential. In addition, all information developed during the conduct of the clinical investigation of the study agent is also considered confidential. Neither the Investigator nor any of his/her employees or agents shall disclose or use this information for any purpose other than the performance of the clinical study. Such information shall remain the confidential and proprietary property of Pulmotect, and disclosure to others will be limited to other physicians who are conducting studies with the same active study agent, the IRB/ethics committee, and the applicable regulatory authorities, except by prior written permission of Pulmotect or its agents. At such time that information becomes widely and publicly available through no fault of the Investigator, the obligation of nondisclosure toward that particular information will cease.

7.3 PULMONARY FUNCTION TESTING	19
7.4 VITAL SIGNS	19
7.5 OTHER SAFETY MEASURES	19
8. INTERIM ANALYSES	20
9. SAMPLE SIZE AND POWER CALCULATIONS	20
10. REFERENCES	20
11. APPENDIX	21
11.1 Appendix A: Schedule of Events	21

LIST OF ABBREVIATIONS

Abbreviation	Definition
ADL	Activities of Daily Living
AE	Adverse event
ATC	Anatomical, Therapeutic, and Chemical
BMI	Body mass index
CI	Confidence interval
СМН	Cochran-Mantel-Haenszel
CTCAE	Common Terminology Criteria for Adverse Events
COVID-19	Coronavirus Disease 2019 caused by the SARS-CoV-2 virus
DSMB	Data and Safety Monitoring Board
eCRF	Electronic Case Report Form
FEV1	forced expiratory volume in 1 second
ICU	Intensive care unit
ITT	Intention to Treat
MedDRA	Medical Dictionary for Regulatory Activities
mITT	Modified Intention to Treat
ODN	ODN M362
Pam2	Pam2CSK4
PI	Principal Investigator
РТ	Preferred term
PUL-042	drug product consisting of a 4:1 molar ratio of Pam2:ODN; Inhalation Solution
SAE	Serious adverse event
SAF	Safety
SAP	Statistical analysis plan
SARS-CoV-2	Coronavirus causing COVID-19
SOC	System organ class
TEAE	Treatment-emergent adverse event
WHO	World Health Organization

1. INTRODUCTION

This statistical analysis plan (SAP) is based on the Protocol # PUL-042-501 Version 1.60, dated 19 January 2021, and titled "A Phase 2 Multiple Dose Study to Evaluate the Efficacy and Safety of PUL-042 Inhalation Solution in Reducing the Infection Rate and Progression to COVID-19 in Adults Exposed to SARS-CoV-2." See the study protocol for full details.

This document details the statistical methods planned to perform the analysis for Data Safety Monitoring Board (DSMB), as well as the final analysis of the study.

2. OBJECTIVES AND ENDPOINTS

2.1 Objectives

2.1.1 Primary Objective

To determine the efficacy of PUL-042 Inhalation Solution in the prevention of viral infection with SARS-CoV-2 and progression to COVID-19 in subjects: 1) who have repeated exposure to individuals with SARS-CoV-2 infection, and 2) are asymptomatic at enrollment.

2.1.2 Secondary Objectives

- To determine the difference in incidence of SARS-CoV-2 infection 28 days from the start of experimental therapy in subjects who test negative for SARS-CoV-2 at the pre-treatment visit
- To determine the difference in incidence of SARS-CoV-2 infection 14 days from the start of experimental therapy in subjects who test negative for SARS-CoV-2 at the pre-treatment visit
- To compare the severity of COVID-19 within 14 days from the start of experimental therapy
- To compare the severity of COVID-19 within 28 days from the start of experimental therapy
- To assess the requirement for ICU admission within 28 days from the start of experimental therapy
- To assess the requirement for mechanical ventilation within 28 days from the start of experimental therapy
- To assess mortality within 28 days from the start of experimental therapy
- To determine the tolerability of PUL-042 Inhalation Solution in this population

2.2 Endpoints

2.2.1 Primary Efficacy Endpoint

The primary endpoint is the severity of COVID-19 as measured by the maximum difference from the baseline value in the Ordinal Scale for Clinical Improvement within 28 days from the start of experimental therapy.

CONFIDENTIAL

2.2.2 Secondary Efficacy Endpoints

The secondary efficacy endpoints include the following:

- Incidence of SARS-CoV-2 infection 28 days from the start of experimental therapy in subjects who test negative for SARS-CoV-2 at the pre-treatment visit
- Incidence of SARS-CoV-2 infection 14 days from the start of experimental therapy in subjects who test negative for SARS-CoV-2 at the pre-treatment visit
- Severity of COVID-19 as measured by the maximum difference from the baseline value in the Ordinal Scale for Clinical Improvement within 14 days from the start of experimental therapy.
- Ordinal Scale for Clinical Improvement within 28 days from the start of experimental therapy
- SARS-Cov-2 Symptom Score during the study
- Proportion of subjects requiring ICU admission from Day 1 to Day 29
- Number of ICU Days from Day 1 to Day 29
- Proportion of subjects requiring mechanical ventilation from Day 1 to Day 29
- Number of days on mechanical ventilation from Day 1 to Day 29
- All-cause mortality rate through Day 29

2.2.3 Safety and Tolerability Endpoints

- Reduction in forced expiratory volume in 1 second (FEV1) from Pre-dose to Post-dose
- Treatment-emergent serious adverse events (SAEs) through Day 29
- Treatment-emergent adverse events (TEAEs) and severity through Day 29
- Vital signs

3. INVESTIGATIONAL PLAN

3.1 Study Design

This will be a double-blind trial. A total of approximately 200 subjects randomized 1:1 (PUL-042 Inhalation Solution: placebo) will be enrolled in the trial.

Doses will be administered via nebulization with a PARI Sprint nebulizer. All subjects will receive up to 4 doses of PUL-042 Inhalation Solution or placebo over 10 days (Days 1, 3, 6, and 10).

Subjects will participate for approximately 28 days. See Appendix A for the Schedule of Events.

An overview of the study design is presented below:

3.2 Treatment

3.2.1 Randomization Scheme and Treatment Arm Assignment

Subjects will be randomly assigned to receive PUL-042 Inhalation Solution or placebo in a 1:1 ratio. A central randomization system, the Medication Assignment Center (MAC; CTI Clinical Trial and Consulting Services), will be used for this study.

3.2.2 Blinding

The sponsor, subjects, Principal Investigator (PI), and site study staff (except for the unblinded study drug personnel) will not know the treatment (PUL-042 vs. placebo) a subject receives. The CRO staff dealing with blinded site study staff and the study statistician will also be blinded. The statistician who generates the production randomization code, MAC Operators who perform the randomization and the unblinded study team will be unblinded to the treatment a subject receives.

All doses of study drug (i.e., both Active and Placebo) will be prepared at the site, so the site Pharmacists will also be unblinded.

3.2.3 Dosing Schedule

The dose level of PUL-042 Inhalation Solution in this study will be 20.3 μ g Pam2 : 29.8 μ g ODN/mL (50 μ g PUL-042). A total of up to 4 doses will be administered over a 10-day period for a total dose of 81.2 μ g Pam2 : 119.2 μ g ODN.

Doses of PUL-042 or placebo will be prepared by an unblinded pharmacist and administered to the subject within 4 hours of preparation.

Doses will be administered via nebulization to deliver 4 mL using a PARI Sprint nebulizer equipped with a filter valve to prevent aerosol generation. The nebulizer will be operated until all drug is delivered.

3.2.4 Subject Compliance

Any material deviation from study procedures (identified by site personnel or monitor) will be documented. Major subject-level deviations will be captured on the protocol deviation form. A list of protocol deviations will be compiled and reviewed by the PI and Sponsor to identify major and minor deviations periodically using the criteria specified in the Protocol, Section 14.5.

4. GENERAL CONSIDERATIONS FOR DATA ANALYSIS

Unless otherwise specified, continuous variables will be summarized using descriptive statistics (n, mean, standard deviation, median, minimum, and maximum). Categorical variables will be summarized showing the number and percentage of subjects within each category.

Summary results will be provided for each treatment group. All tabulations will be based on pooled data across centers.

Unscheduled visits will be excluded from the summaries but will be included in the data listings.

All statistical tests will be two-sided and tested at the 10% level of significance.

Analyses will be performed using SAS for Windows statistical software, version 9.4 or higher (SAS, Cary, NC), except where other software may be deemed more appropriate.

CTI will perform all efficacy and safety analyses described in this SAP.

Subject data will be listed, sorted by treatment group and subject number. When applicable, listings will be additionally sorted by visit and assessment date/time.

4.1 Data Quality Assurance

Once all the source verification is complete, all queries are resolved, and the database has been updated appropriately, the database will be locked and made available to CTI Biostatistics for final analysis.

Data may be pulled by CTI Biostatistics for DSMB analysis at a time when source verification and query resolution is ongoing.

All SAS programs used to create analysis data sets, tables, and listings are double programmed. The SAS outputs will be compared and the programs will be updated until the outputs match.

4.2 Analysis Sets

The following three analysis sets will be defined for this study:

Intent to Treat (ITT) Set

The ITT set is defined as all randomized subjects who receive at least one dose of experimental treatment (i.e., PUL-042 or Placebo). Randomized subjects are to be symptoms free and not known to be SARS-CoV-2 positive at baseline. The primary analysis of the efficacy endpoints will be carried out using the ITT set based on the randomized treatment, except for the first two secondary efficacy endpoints listed in Section 2.2.2.

Modified Intent to Treat (mITT) Set

The mITT set will include all randomized subjects who receive at least one dose of experimental treatment (i.e., PUL-042 or Placebo) and are negative for SARS-CoV-2 infection at the time of administration of the first dose.

The mITT set will be used for the analyses of the first two secondary efficacy endpoints listed in Section 2.2.2.

Safety (SAF) Set

The SAF set is also defined as all randomized subjects who receive at least one dose of experimental treatment (i.e., PUL-042 or Placebo), but subjects are categorized based on the treatment actually received rather than as randomized. All safety and tolerability analyses will be carried out using the SAF set. If, as is expected, the Safety analysis set is redundant (i.e., is identical to the ITT analysis set), the ITT set will be used for the assessments of safety and tolerability.

4.3 Assessment Windows

Data will be summarized by nominal study visit recorded in the database.

4.4 Handling of Dropouts or Missing Data

Except for the time to event endpoint (Table 1), partial end dates of prior and concomitant medications (Section 5.6), and partial onset dates of AEs (Section 7.2.1), all other missing data will be treated as missing and no method for imputation is planned.

Missing data on the time to event endpoint will have events coded as right censored per the following table:

Table 1 Missing Data Coding for Time to Event Data Analysis

Endpoint	Right Censoring
Subject Survival	Subjects who are still alive as of the last known follow-up will be
	right censored as of the date of last subject contact when the subject
	was known to be alive.

4.5 Multiple Comparisons

Because of the exploratory nature of this study, there will be no adjustment for multiple comparisons.

4.6 Data Derivations and Transformations

The following derivations will be used in this study:

Study Day (Note: There is no day 0 in this study):

- Date of assessment date of 1st Study Drug administration + 1 for assessments done on or after date of 1st Study Drug administration
- Date of assessment date of 1st Study Drug administration for assessments done before date of 1st Study Drug administration

Baseline Observation: the last non-missing value prior to 1st Study Drug administration.

Duration:

- Duration in days = end date start date + 1
- Duration in minutes = end time in minutes start time in minutes

5. STUDY SUBJECTS

5.1 Disposition of Subjects

A table of frequency counts and percentages of all subjects who are randomized, and in each analysis set will be provided. Subject disposition including study completion status and reasons for early termination will be tabulated by treatment group and overall. A by subject listing will be provided.

CONFIDENTIAL

5.2 **Protocol Deviations**

Distribution of the types of protocol deviations and the number of subjects that deviate from the protocol will be tabulated for the treatment groups in the ITT set. Protocol deviations will also be tabulated by severity (e.g., minor or major) if appropriate. A listing of all protocol deviations will be provided.

5.3 Demographic Characteristics

Descriptive statistics will be used to summarize the demographic characteristics (age, gender, race, ethnicity, height, weight, and Body Mass Index [BMI]) for the ITT set. A by subject listing will be provided.

5.4 **Baseline Characteristics**

Baseline characteristics of ITT subjects including SARS-CoV-2 exposure and spirometry results at Screening will be listed and tabulated.

5.5 Medical History

All medical conditions and surgical procedures will be classified by system organ class (SOC) and preferred term (PT) using the Medical Dictionary for Regulatory Activities (MedDRA). The number and percent of subjects with each medical condition and surgical procedure will be presented for each SOC and PT for the ITT set.

5.6 Concomitant Medications and Procedures

All concomitant medications collected will be coded using the World Health Organization (WHO) Drug Dictionary. The number and percent of ITT subjects using concomitant medications will be tabulated by Anatomical, Therapeutic, and Chemical (ATC) level 2 and by preferred name. If the ATC level 2 is missing, the higher ATC level term will be used in the medication summary table and data listing.

A listing of all medications will be provided. The listing will include flags for prior medications.

Prior medications are defined as medications that ended prior to the date of first Study Drug administration. Concomitant medications are defined as medications that started at any time but ended on or after the date of first Study Drug administration, including those that are ongoing at study completion. In the case of a partial end date/time, in order to determine whether a medication is prior or concomitant, the following conservative imputation rule will be used: the unknown portions of a medication end date will be imputed to the latest possible. The imputed medication end date will then be compared with the date of first Study Drug administration to determine if the medication is prior or concomitant.

Note the imputed end date will only be used to determine whether a medication is prior or concomitant. The actual date reported on the electronic case report forms (eCRFs) will be presented in the listing.

Concomitant procedures will be collected via free text in the eCRF. These data will be presented in a listing.

6. EFFICACY ANALYSES

Data on all efficacy endpoints will be listed and tabulated as appropriate.

6.1 **Primary Efficacy Endpoint and Analysis**

The primary efficacy analysis will be carried out on the ITT set.

The primary efficacy variable is the severity of COVID-19 as measured by the maximum difference from the baseline value in the Ordinal Scale for Clinical Improvement within 28 days from the start of experimental therapy. Randomized subjects are to be symptoms free and not known to be SARS-CoV-2 positive at baseline.

The Ordinal Scale for Clinical Improvement is a 9-point scale that measures disease severity at a given point in time. Notably, a score of 0 indicates that an individual is infection-free. The difference in scores obtained at different times provides a quantitative assessment of the incidence of infection and change in disease severity over that time interval.

The Ordinal Scale for Clinical Improvement to be used in this study is derived from a draft scale proposed by the World Health Organization^[1] for clinical improvement as presented below:

Descriptor	Score	
No clinical or virological evidence of infection	0	
Infected but no limitation of activities	1	
Limitation of activities	2	
Hospitalized not requiring oxygen therapy (SpO2 > 93% on room air)	3	
Oxygen by mask or nasal prongs	4	
Non-invasive ventilation or high-flow oxygen	5	
Intubation and mechanical ventilation	6	
Ventilation + additional organ support- pressors, RRT, ECMO	7	
Death	8	

Table 2 Ordinal Scale for Clinical Improvement (Derived from draft WHC)) scale)[1]
---	-------------

The null hypothesis is that there is no difference in mean maximum change in Ordinal scale from baseline through Day 29 between randomized treatment groups; H₀: $\Delta_t - \Delta_c = 0$. The alternative hypothesis is that the mean maximum change in Ordinal scale from baseline through Day 29 are different between the treatment groups; H₁: $\Delta_t - \Delta_c \neq 0$.

The change in severity of COVID-19 between the placebo- and actively-treated groups will be compared using an analysis of covariance (ANCOVA) model, including the maximum change in

Ordinal scale from baseline through Day 29 as a dependent variable, treatment group as a fixed effect, and baseline characteristics such as age as a covariate.

From this model, the least-squares (LS) means and 90% CIs for each treatment group, the treatment difference in the LS means, the 90% CI for the difference, and the associated p-value will be presented.

If the data cannot support ANCOVA model assumption, a sensitivity analysis will be performed using proportional-odds cumulative logit model. The cumulative logits model will compare lower ordinal scales to higher ones, or equivalently, more favorable outcomes to less favorable ones. The model may be adjusted for baseline characteristics such as age, if appropriate. The estimated odds ratio and 95% CI will be presented.

The proportional odds assumption will be tested using a score test at the two-sided alpha level of 0.05. In the event that the proportional odds assumption is not satisfied, given the anti-conservative nature of the score test, the proportional odds model will still be used for the analysis, and the results will be presented along with the score test p-value to help put these results in context. If the proportion odds assumption is rejected or if the proportional odds model fails to converge, an alternative analysis using Cochran-Mantel-Haenszel (CMH) test will be performed to evaluate the association between the treatment groups and the maximum change in ordinal scale from baseline. The p-value for CMH row mean scores statistic will be reported.

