6.2 Secondary Efficacy Endpoints and Analyses

Incidence of SARS-CoV-2 infection through Day 29

The analysis of the proportion of subjects who had a positive result from the SARS-CoV-2 test within 28 days from the first dose of study drug will be performed using the mITT set.

The null hypothesis is that there is no difference in proportions of subjects with SARS-CoV-2 infection through Day 29 between randomized treatment groups; H₀: $\pi_t - \pi_c = 0$. The alternative hypothesis is that the proportions of subjects with SARS-CoV-2 infection through Day 29 are different between the treatment groups; H₁: $\pi_t - \pi_c \neq 0$.

The proportion of mITT subjects with SARS-CoV-2 infection within each treatment group will be presented along with a two-sided exact (Clopper-Pearson) 90% confidence interval (CI).

The observed difference in the proportion of subjects with SARS-CoV-2 infection between treatment groups along with the exact unconditional 90% CI for risk difference will be calculated. The null hypothesis will be tested using Fisher's exact method and the p-value will be reported.

Incidence of SARS-CoV-2 infection through Day 15

The analysis of the proportion of mITT subjects who had a positive result from SARS-CoV-2 test within 14 days from the first dose of study drug will be performed using the method described above for the analysis of incidence of SARS-CoV-2 infection through Day 29.

Severity of COVID-19 through Day 15

The change in severity of COVID-19 from baseline through Day 15 between the treatment groups will be compared using an ANCOVA model, including the maximum change in Ordinal scale from baseline through Day 15 as a dependent variable, treatment group as a fixed effect, and baseline

characteristics such as age as a covariate.

From this model, the least-squares (LS) means and 90% CIs for each treatment group, the treatment difference in the LS means, the 90% CI for the difference, and the associated p-value will be presented.

If the data cannot support ANCOVA model assumption, a sensitivity analysis will be performed using proportional-odds cumulative logit model as described above for the primary efficacy endpoint analysis.

Ordinal Scale through Day 29

The absolute value and change from baseline in the Ordinal scale from Day 1 through Day 29 will be summarized by treatment group and visit using descriptive statistics.

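### The primary and Day 15 severity models do not prespecify the Day 1 swab result, and no supplied text says how a late-reported swab sets the ordinal score at 0 or 1

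*SAP*

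**What the plan says.** **Who is analysed.** SAP 6.1 runs the primary analysis on the ITT set (randomized and dosed at least once) and adds: "Randomized subjects are to be symptoms free and not known to be SARS-CoV-2 positive at baseline". Protocol 7.10.1 takes the first swab on Day 1 before dosing, and Protocol 8.4 sends it to a central laboratory. No turnaround time is given, and nothing makes dosing or scoring wait for the result.

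**Where the Day 1 result is used.** It defines the mITT set. SAP 4.2 limits that set: "The mITT set will be used for the analyses of the first two secondary efficacy endpoints listed in Section 2.2.2". Those two endpoints are infection incidence, not severity.

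**What the models name.** The primary ANCOVA has treatment and "baseline characteristics such as age as a covariate". The Day 15 severity model in SAP 6.2 likewise has "characteristics such as age as a covariate". Protocol 13.3 gives the baseline ordinal score as one example covariate, which the SAP does not repeat. Neither document names the Day 1 swab result.

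**How the scale is scored.** SAP 6.1 states: "Notably, a score of 0 indicates that an individual is infection-free". In its table, score 0 requires that both clinical and virological evidence be absent, and score 1 is infection without limitation. Inclusion criterion 3 (Protocol 7.2.1) ties score 0 to the absence of signs or symptoms. SAP 4.6 defines "Baseline Observation: the last non-missing value prior to 1st Study Drug administration". The scale is scored at screening and on Days 1, 3, 6, 10, 15 and 29. Swabs are scheduled on Days 1, 15 and 29, with extra tests when symptoms suggest COVID-19.

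**The concern.** Entry rests on recent exposure, including cohabitation with an infected person, so some subjects will probably be infected but asymptomatic on Day 1. If their baseline is recorded as 0, each adds at least +1 to the primary endpoint once the infection is scored. Treatment cannot prevent that infection. These subjects add variance, and a chance imbalance in their number between the arms moves the treatment estimate. The information that would remove this noise is already collected before treatment and is not used.

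The second gap concerns data collection. An asymptomatic subject whose swab is pending at the visit fits score 0 on clinical grounds. Once the swab reads positive, the same visit fits score 1. The documents do not say whether the score is updated, or whether the sample date or the result date governs. The 0/1 boundary is where an asymptomatic infection enters the primary endpoint, so different site habits would give like subjects different values.

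**Working it through.** **1. Inputs.** From the documents: 100 per arm (SAP 9), 1:1 allocation, two-sided 10% level (SAP 4). SAP 9 says infection rates are unknown, and there is no power figure to reproduce. Everything else is assumed:
- placebo attack rate among Day 1 negatives p = 15% or 20%;
- risk ratio 0.4, 0.5 or 0.7;
- Day 1-positive share f = 2-20%;
- no effect in those already infected;
- maximum score if infected: 1, 2, 3, 4, 6, 8 with probability 55, 35, 5, 3, 1, 1%.

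That distribution has mean 1.66, mean square 3.88 and variance 3.88 - 1.66² = 1.124.

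**2. Hand calculation (f = 10%, p = 15%, risk ratio 0.4; all Day 1 positives later scored, baseline 0).**
- True difference: 0.9 × (0.15 - 0.06) × 1.66 = 0.134.
- Placebo: mean 0.1 × 1.66 + 0.9 × 0.15 × 1.66 = 0.390; variance 0.388 + 0.524 - 0.390² = 0.760.
- Active: mean 0.256; variance 0.388 + 0.210 - 0.256² = 0.532.
- Unadjusted SE: √((0.760 + 0.532)/100) = 0.114. Power ≈ Φ(0.134/0.114 - 1.645) ≈ 32%.
- Variance among Day 1 negatives: placebo 0.582 - 0.249² = 0.520; active 0.233 - 0.100² = 0.223; average 0.371.
- Adjusted residual variance: 0.1 × 1.124 + 0.9 × 0.371 ≈ 0.447. SE = √(2 × 0.447/100) = 0.095. Power ≈ 41%.
- The SE falls by 17%.
- If baseline is re-scored to 1 for all Day 1 positives, the unadjusted SE is already 0.097, so adjustment adds little. The placebo mean change drops from 0.390 to 0.290 for identical patients.

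Chance imbalance explains the loss. The 95% range for the between-arm difference in Day 1 positives is ±1.96 × √(2 × 0.1 × 0.9/100) = ±8.3 percentage points. Positives exceed negatives by about 1.66 - 0.17 = 1.49 in mean change, so this alone can move the estimate by 0.083 × 1.49 = 0.12, nearly the true difference.

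**3. Simulation (6,000 trials per cell, risk ratio 0.4; power in %).** The normal approximation runs slightly low because the scores are skewed.

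| Attack rate | Day 1 positive | Baseline 0, unadjusted | Adjusted for Day 1 result | Re-scored to 1, unadjusted |
|---|---|---|---|---|
| 15% | 2% | 49.9 | 54.7 | 53.4 |
| 15% | 5% | 43.2 | 51.7 | 50.8 |
| 15% | 10% | 34.1 | 44.5 | 43.1 |
| 15% | 20% | 24.3 | 34.5 | 32.9 |
| 20% | 2% | 62.8 | 66.5 | 66.0 |
| 20% | 5% | 54.9 | 62.6 | 61.3 |
| 20% | 10% | 44.7 | 55.1 | 53.5 |
| 20% | 20% | 32.2 | 44.8 | 43.1 |

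A CMH test stratified by the Day 1 result gains the same within 0.2 points. At risk ratio 0.5 the gain is 3-9 points. At 0.7, with 2-10% positive, it is about 1-3. If only 60% of Day 1 positives later score at least 1, at 10% positive, power goes from 39.2 to 43.5% (attack rate 15%) or from 51.1 to 54.5% (20%). Null rejection was 9.2-10.8% throughout. The Day 15 model was not simulated separately.

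**4. Mixed baseline scoring.** If every Day 1 positive gets the same baseline score, the adjusted estimate is identical whether that score is 0 or 1. With a random half at each (f = 10%), the adjusted estimate moves by about 0.018 on average, against a true difference of 0.134, and power falls by about 1.5-3 points. Carrying the baseline ordinal score as well restores it.

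**5. Proportional-odds model.** SAP 6.1 states: "The proportional odds assumption will be tested using a score test at the two-sided alpha level of 0.05". Without a Day 1 term that test rejected in 3-6% of simulated trials. With the term, baseline 0 and every Day 1 positive later scored, it rejected in 19-24% at 2% positive and 87-91% at 10%. If 60% are later scored, it rejected in about 5-15% at 2-10% positive (200-250 trials per cell).

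**The case against.** Several counter-arguments stand in part.
- **Inclusion is deliberate.** The ITT wording shows that the authors accepted undetected positives. The objective covers progression as well as infection, and Protocol 7.8 lets subjects who turn positive continue dosing. Assuming no effect in those already infected therefore leaves out part of the objective. This limits the power figures but does not argue against adjusting for a pre-treatment variable.
- **The covariate list is open.** The Day 1 result is not ruled out. But an open list leaves the choice to be made later, which a SAP is meant to settle.
- **The descriptors already exclude score 0 once there is virological evidence.** True; only the rule for timing is missing. It may be in the Laboratory Manual or other site instructions, which were not supplied.
- **The gain may be small.** It is, at weak effects, with few Day 1 positives, or with a uniformly re-scored baseline.

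A reader might infer stronger conclusions that the documents do not support:
- *The primary analysis is biased, or ITT is the wrong set.* Randomization protects the comparison, and null rejection stays near 10%.
- *Adjusting for the swab makes the baseline score irrelevant, so the baseline ordinal score can be dropped.* That holds only under uniform scoring, which no supplied text ensures.
- *The Day 1 term must be kept out of the proportional-odds model.* The high rejection rates need nearly every Day 1 positive to score at least 1 later. SAP 6.1 also keeps that model after rejection and adds the CMH test: "If the proportion odds assumption is rejected or if the proportional odds model fails to converge".

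**Conclusion.** Both gaps are real on the supplied text. The first is a precision gain left unused, and the second is an unstated scoring convention at the lowest step of the primary endpoint. Neither affects type I error or calls for a different primary set.

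Under the assumptions in the working, with baseline 0 and all Day 1 positives later scored, the gain is about 4-13 power points at risk ratio 0.4 and 3-9 at 0.5 (2-20% positive). The smaller gains at 0.7 (about 1-3), with 60% later scored (about 1-4) and with a uniformly re-scored baseline (under 2) are equally compatible with the documents, which give no rates. This is a cheap improvement of minor to moderate weight. Confidence is high on the text and medium on the size.

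**What to change.** 1. In SAP 6.1 and in the Day 15 severity analysis of SAP 6.2, name the Day 1 SARS-CoV-2 result (positive, negative, unknown) as an ANCOVA covariate and as the stratum in the CMH test. The baseline ordinal score, already an example in Protocol 13.3, may be carried too, and should be if baseline scores vary among Day 1 positives.
2. State one rule for how a swab reported after a visit sets score 0 or 1, at baseline and at every later visit, including symptom-triggered tests. Apply it uniformly, refer to it in SAP 4.6, and fix it before unblinding. If a site manual already holds the rule, a cross-reference is enough.
3. Leave adjustment of the proportional-odds sensitivity model for the Day 1 result optional, noting that proportional odds may fail for that term if nearly all Day 1 positives later score at least 1.

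ITT stays primary. The cost is SAP wording, one model term, one stratum and one scoring rule, with no new data. The downsides are the unknown level (with 5% of Day 1 results missing at random, power falls 0.4-1.1 points against complete results) and little return if few subjects are positive on Day 1.
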